Addback. After 6-weeks of Lupron-alone treatment (i.e., hypogonadism), physiological plasma levels of E2 and P4 will be attained via micronized E2 and P4 tablets for two weeks (with continued Lupron administration), respectively. E2 and P4 will be administered in a double-blind, cross-over design with a 2-week washout period in-between E2 and P4 administration. E2 will be administered at a dose of 2 mg bid (i.e., a total of 4 mg per day). P4 will be administered at a dose of 200 mg bid (i.e., a total of 400 mg per day). The blood levels that we expect to achieve and

| | |
|----------------------------|--|
| | sustain in each woman will be approximately 500 pg/ml of E2 and 30-40 ng/ml of P4. |
| Duration of administration | 3 months |
| Reference therapy | Placebo |
| Statistical Methodology | A 2 x 2 double-blind crossover design, with 2-sequence, 2-period and 2-treatment will be implemented |

1 Introduction

This document is a protocol for a human research study. This study is to be conducted according to US and international standards of Good Clinical Practice (FDA Title 21 part 312 and International Conference on Harmonization guidelines), applicable government regulations and Institutional research policies and procedures.

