Cumulatively, it appears that low E2 or P4 antagonized E2 (both E2 and P4 are *high*) are risky milieus for binge eating.¹¹ The exact hormone milieu that is “risky” may depend on the level of pathology present: subsetting a community sample into DSM-defined binge eaters vs. non- binge eaters showed a significant inverse main effect for E2.¹² This suggests that for those with higher levels of pathology, low E2 may be the catalyst for symptom exacerbation. In contrast, the follicular and ovulatory phases may be protective: across all studies, binge-eating frequency is lowest during these phases.^{5, 6, 13-15} During the follicular phase, E2 is rising in preparation for ovulation and reaches peak levels at ovulation whereas P4 is low and relatively stable. Finally, two recent case reports show manipulation of E2/P4 directly effects symptomatology. The introduction of a P4-only hormonal contraceptive relapsed gains made in treatment for BN, which was reversed upon stopping the medication.¹⁶ Impressively, complete recovery from subclinical binge eating disorder was also achieved following surgical ovarian suppression (i.e., bilateral salpingo-oophorectomy and hysterectomy) treatment for PMDD,¹⁷ which results in the absence of E2/P4. This could suggest that, unlike animals, hypogonadism may result in symptom relief for humans: hormone sensitivity may reflect sensitivity to *changing* levels vs. the presence (or absence) of acute levels. This is corroborated by the fact menopause (i.e., hypogonadism) does not

result in increased ED symptoms, yet the menopause transition (i.e., chaotic changes in ovarian hormones) does.¹⁸

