Figure 1. Hypothesized cycle of the effect of E2 on binge eating

behavior, which is modulated by cycling E2 (Figure 1). Decreasing E2 triggers a cascade of neurobiological events leading to the onset of or increased engagement in reward-motivated behaviors (i.e., binge eating) in vulnerable women (i.e., low dopamine activity). While others made postulations regarding reward-related inhibitory control,^{24, 34, 81} few considered the effect of E2.^{25, 82-84} Although some,⁸⁵ but not all,⁵ studies suggest dysregulated hormone levels in women with BN, we do not hypothesize physiologically aberrant ovarian hormone levels are a precursor to BN, rather behavioral reactions to normal hormone changes are dysregulated in women with [or at risk for] BN due to an underlying sensitivity to this change. Currently, research in this area focuses on E2 and overlooks P4; assuming that the effect of P4 is indirect and not causal. However, we could be overlooking an important etiological construct given P4 also directly impacts dopamine levels,⁸⁶ which are at the core of our hypothesized model.

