Addback. After 6-weeks of Lupron-alone treatment (i.e., hypogonadism), physiological levels of E2 or P4 will be attained via oral micronized E2 (2mg b.i.d) or P4 (200mg b.i.d), respectively (along with continued Lupron administration), with a 2-week washout period in-between. Placebo pills continue during the washout. Each addback phase will be 2-weeks (compared with 4-weeks) as previous studies using this experimental design have shown significant symptom change can be obtained within 2-weeks.⁸⁷ Subjects will be randomized to receive E2 followed by P4 or P4 followed by E2. The study biostatistician will create a randomization table and study investigators will be blinded to the randomization order. End-of-phase assessments will occur at the end of E2 and P4 addback (T3/T4).

Once medication administration begins, subjects will be instructed to take pills twice daily, at approximately the same time each day. To improve medication compliance, we will recommend subjects schedule a daily reminder on their phone to take the study medication each day. The daily assessments will also ask participant’s whether they took the study medication each day.

Clinical Assessments. Measures used to obtain primary outcomes and monitor subject safety are shown in **Table 4**. Study visits will occur every 2-weeks. Participants will attend end-of-phase assessments at the end of each hormone phase as well as check-in visits to monitor symptoms. There will be an equal number of end-of-phase assessments and check-in visits (3 each) during the hormone challenge. All study measures are empirically valid and reliable.

Clinical Interviews

- a) **SCID-5:** Structured Clinical Interview for DSM-5¹⁸¹ will be administered by trained study staff at T0, and supervised by [name], to confirm eligibility and BN diagnosis. Based on DSM-5 criteria, the interview guides trained interviewers in determining whether a psychiatric diagnosis is present or absent.

Self-report Questionnaires

Self-report questionnaires will be completed through secure, encrypted, online survey (i.e., Qualtrics), and scored by standard conventions. During the reproductive hormone challenge, (i.e., T1-T4) self-report questionnaires will be modified to represent symptomatology over the previous week only, in order to capture the period of time with maximal or minimal pathology during each hormone manipulation phase.

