The BIS/BAS and SPSRQ will be included as a self-report measures of reward response. Specifically, we will include the reward responsiveness, behavioral inhibition, and fun seeking subscales of the BIS/BAS as self-report correlates of the reward response. The SPSRQ will be used to assess sensitivity to reward.

Hypothesis. Our overarching hypothesis for the following aims is that BN represents a hormone sensitive phenotype and this sensitivity is displayed as an impaired reward response within the context of low E2 such that E2 addback will be beneficial for all outcomes of interest (i.e., binge eating, aspects of the reward response). As such, our null hypothesis is that there is no effect of E2 on binge eating or the reward response. For all hypothesis tests, we will use the Benjamini-Hochberg Procedure to correct for multiple comparisons.

Aim 1: Quantify the direct effect of E2 and P4 on binge eating in women with BN.

Dependent variables: EPSI binge eating subscale score; DSRP binge eating weekly average.

Independent variables: Treatment sequence, treatment condition, and selected covariates

The two longitudinal measures of binge eating (i.e., EPSI subscale score and DSRP weekly average) will be fit to linear mixed effect models with subject-specific random intercept assuming an unstructured covariance among different time points. Such a covariance allows different variance and covariance parameters to be estimated for each time point allowing for potential increasing or decreasing variability in outcomes during each of the follow-up time points for each outcome and will include fixed effect predictors such as binary treatment sequence (E2-P4 or P4-E2) and treatment condition of categorical variable with three levels: Lupron-alone, E2, or P4, where effect size and standard error of fixed effect parameters will be estimated in the described model followed by t -test. Study hypotheses comparing outcomes between group outcomes of E2 vs. Lupron-alone, E2 vs. P4, and P4 vs. Lupron-alone, will be tested using contrasts test through t -test of least squares means estimate in the context of the main effects model.

Along with the primary contrasts of interest described above, additional contrasts between each end point of treatment condition (Lupron-alone, E2, or P2) and baseline (T1), which occurs prior to medication administration, will be tested using the statistical model just described above.

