Aim 2: Determine the effect of E2 on reward response and related correlates (e.g., behavioral inhibition) in women with BN.

Dependent variables: Behavioral measures of reward response, self-report measures of reward response.

Independent variables: Treatment sequence, treatment condition, and selected covariates

Behavioral measures of reward response (MID, DD) and related correlates (Go No/Go, BIS/BAS, SPSRQ) will be fit to linear mixed effect models as described above with binary treatment sequence (E2-P4 or P4-E2), treatment condition, and covariates as independent variables and reward response as dependent variables. The contrasts between E2 and baseline (T1) or Lupron-alone (T2) will be tested in the same model.

For the behavioral tasks, beneficial impacts of E2 are defined as an accelerated speed of response to rewards and improvement in reward learning during the MID, higher indifference points during the DD task, and fewer errors on the Go No/Go Task. For self-report questionnaires, a decrease in scores represents a beneficial response as higher scores indicate more “pathological” responses.

Aim 3: Examine the association between reward response (defined in Aim 2) and binge eating before and after E2 addback.

Null hypothesis: There is no association between reward response and binge eating before and after E2 addback
Alternative hypothesis: There is an association between reward response and binge eating before and after E2 addback.

We will explore Pearson correlations between change in self-reported reward responses and change in binge eating between baseline and E2 addback. Binge eating will be defined by the EPSI subscale score. Reward response will include the BIS/BAS reward responsiveness subscale, and SPSRQ reward sensitivity subscale. Specifically, a change score will be created that signifies the amount and direction of change that occurred in binge eating and reward responses between baseline and E2 addback for each subject. A Pearson correlation will then be examined between binge eating and reward response change scores.

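### E2 and P4 versus Lupron-alone, and every contrast with T1, compare a later visit with an earlier one, and the models name no period or time term

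*Combined protocol and SAP*

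**What the plan says.** The Study Summary states: "A 2 x 2 double-blind crossover design, with 2-sequence, 2-period and 2-treatment will be implemented". Section 5.3 allocates 8 women to E2-P4 and 7 to P4-E2.

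Under section 7.2, Aim 1, the main-effects model contains "fixed effect predictors such as binary treatment sequence (E2-P4 or P4-E2) and treatment condition of categorical variable with three levels: Lupron-alone, E2, or P4", fitted "assuming an unstructured covariance among different time points". The hypotheses "E2 vs. Lupron-alone, E2 vs. P4, and P4 vs. Lupron-alone, will be tested using contrasts test", with further contrasts of each condition against T1. For Aim 2, "The contrasts between E2 and baseline (T1) or Lupron-alone (T2) will be tested in the same model"; no other contrast is named there. The example covariates are negative affect and food intake. The sensitivity paragraph mentions modelling assumptions in general, not time or period.

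Section 6 fixes the order. T1 precedes all drug. T2 comes after six weeks of Lupron and before addback. The two addback phases of two weeks each follow, separated by a two-week washout: "Placebo pills continue during the washout". Table 4 schedules EPSI, BIS/BAS, SPSRQ and saliva at check-in visits, one of which falls after the washout. Daily ratings run to T4. The behavioural tasks are not done at the post-washout visit.

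**The concern.** Randomising the order of E2 and P4 balances time between those two conditions. It does nothing for a comparison with T1 or T2, which come first in everyone. Anything that changes over the weeks (suppression still deepening, the course of the illness, repeated questionnaires, practice on the tasks) is then counted as an effect of E2 or P4. For the tasks, Aim 2 defines benefit partly as faster responses and fewer errors, which practice could also produce.

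Sequence and condition main effects do not absorb this. In a two-by-two crossover the period effect is the sequence-by-condition interaction, which a main-effects model leaves out. The unstructured covariance describes variances and correlations, not means.

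E2 vs Lupron-alone bears directly on the stated null of no E2 effect, and Aim 2 has only contrasts of this kind. Section 7.1 says the pilot is to supply data for larger studies, so any drift would enter the effect sizes carried forward.

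**Working it through.** **Timeline (sections 3.1 and 6, visits every two weeks).** T1 week 0; T2 week 6; T3 week 8; post-washout check-in week 10; T4 week 12. One step is two weeks.

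**The plan's own figure.** Section 7.1 gives a detectable effect of 0.77 for n = 15, two-sided 5%, 80% power. A paired t-test (df 14) has 79.2% power at 0.77, reaches 80% at 0.778, and has 99.97% power at 1.5, consistent with the stated figure above 90%. So the plan's power calculation matches a paired comparison with no period or time term.

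**Average lag under the planned model.**
- E2 after T2: (8×1 + 7×3)/15 = 29/15 = 1.93 steps
- P4 after T2: (8×3 + 7×1)/15 = 31/15 = 2.07 steps
- E2 after T1: (8×4 + 7×6)/15 = 74/15 = 4.93 steps
- E2 minus P4: 1.93 − 2.07 = −0.133 steps. T3 and T4 are 2 steps apart, so this is 1/15 of the T3-to-T4 period effect.

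**E2 vs Lupron-alone if there is drift and no E2 effect.** Drift sizes are assumptions, in SD of the paired difference per step. The noncentrality is drift × 1.93 × √15, with df = 45 − 17 = 28. The noncentral t ignores the residual variance added by unmodelled drift; simulation (40,000 trials per cell) includes it.

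| Drift per step | Bias (SD) | Noncentrality | Noncentral t | Simulated rejection |
|---|---|---|---|---|
| 0.1 | 0.19 | 0.75 | 11% | about 11% |
| 0.2 | 0.39 | 1.50 | 30% | about 27% |
| 0.3 | 0.58 | 2.25 | 58% | about 51% |

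**What different time terms do** (within-subject least squares, compound symmetry; SE in residual SD; bias in steps).

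| Model | E2 − Lupron bias | SE | E2 − P4 bias | SE |
|---|---|---|---|---|
| Planned | 1.93 | 0.365 | −0.133 | 0.365 |
| + period, T4 indicator | 1.00 | 0.403 | 0 | 0.366 |
| + period, effect-coded | 2.00 | 0.365 | 0 | 0.366 |
| + linear time, no week 10 | 0 | 0.508 | 0 | 0.366 |
| + week 10 and linear time | 0 | 0.338 | 0 | 0.366 |
| + categorical visit | not estimable (rank 18 of 19) | – | 0 | 0.366 |

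A period term therefore repairs E2 vs P4 but leaves 1 to 2 steps of drift in E2 vs Lupron-alone. The zeros for linear time hold only if drift is linear.

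**E2 vs P4 power at 0.77 with an assumed 0.5 SD period effect.** With T3 and T4 only: 67% to 75% without the term, 79% with it. In the three-visit model: 75% to 82% without, 82% with. The ranges are the two signs of the period effect. With no period effect, the term costs almost nothing: 78.5% against 79.2% (T3/T4 only, df 13).

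**Limits of week 10.**
- An effect c at week 10, equal in both sequences, moves the week-10 estimate of E2 vs Lupron-alone by −0.73c. If binge eating worsens after hormone withdrawal, E2 looks better than it is. With no E2 effect and c = 0.5 SD, that model rejects about 31%, while the planned model stays at 5%.
- If withdrawal matters only after E2, the shift is −0.39c, and rejection at 0.5 SD is about 12%.
- A one-off step between weeks 6 and 8 leaves 27% of itself as bias.

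**The case against.** Much can be said for the plan. E2 vs P4, the randomised contrast, is already listed in Aim 1. The model sentence offers its predictors as examples, and the sensitivity paragraph allows alternative modelling assumptions. T2 follows two weeks of blinded placebo capsules, and section 6 sets aside the first month on Lupron as a waiting period. Sections 1.4 and 1.5 describe suppression as induced in six weeks; the two months in section 1.2 is an upper bound that does not contradict this. The study is a proof-of-concept pilot.

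These points limit the weight of the concern. They do not remove it: room for a time term is not a commitment to one, and none of these features alters the fixed order of T1, T2 and addback.

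Three stronger readings are tempting, and the documents support none of them.

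- A reader might infer that drift is present and that an E2 vs Lupron-alone finding would be spurious. No drift, period or practice effect is quantified anywhere in the documents.
- A reader might infer that omitting period seriously biases E2 vs P4. At 8:7 the bias is 1/15 of the period effect, and in the three-visit model power is lost for only one sign of that effect.
- A reader might treat week 10 as a clean control and call E2 vs Lupron-alone robust only if both analyses are significant. The protocol's own theory speaks against this: "Decreasing E2 triggers a cascade of neurobiological events leading to the onset of or increased engagement in reward-motivated behaviors", and "hormone sensitivity may reflect sensitivity to *changing* levels vs. the presence (or absence) of acute levels". Such a rule can also be costly. At a true effect of 0.77 the planned model alone has 82% power and the joint rule 78% if week 10 is clean. The joint figure falls to 69% or 59% if 0.3 or 0.5 SD of the E2 benefit persists at week 10 in the E2-first women. It falls to 57% or 35% with a week-10 shift of those sizes in both sequences in the direction of the E2 effect, and to 56% or 27% with drift of 0.1 or 0.2 opposing it.

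**Conclusion.** The concern holds. A declared two-period crossover is analysed with no period or time term, and the Lupron-alone and T1 contrasts, including every contrast named in Aim 2, are unrandomised in time. Under the planned model they cannot separate hormone from elapsed time.

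The size is conditional: about 11%, 27% or 51% false rejection of E2 vs Lupron-alone at the three assumed drifts. These rates assume linear drift, compound symmetry, complete data and 8:7 allocation, and are per test before Benjamini-Hochberg. For E2 vs P4 the matter is mainly one of precision.

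The omission and the order are certain from the text; whether drift occurs is unknown. Week-10 data can inform the reader but cannot settle the question, because linear drift and the absence of carry-over or withdrawal effects are both untested assumptions. This is a cheap improvement worth making, not a fault that invalidates the design.

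**What to change.** 1. **E2 vs P4.** Test it with a T3/T4 period term. State that this is a separate fit from the one used for the Lupron-alone contrasts, that a period term alone does not remove drift from those contrasts, and that a fully categorical visit term makes E2 vs Lupron-alone non-estimable.
2. **Labelling.** In Aims 1 and 2, describe E2 vs Lupron-alone, P4 vs Lupron-alone and every contrast with T1 as unrandomised before-after comparisons open to time effects, and on MID, DD and Go/No-Go to practice effects as well. The tasks have no week-10 measurement, so this remains a stated limitation for them.
3. **Supportive sensitivity analysis.** For EPSI, the daily binge average, BIS/BAS and SPSRQ, prespecify one model per outcome that adds the week-10 visit as a second Lupron-alone observation with a linear time term. Report its estimate and interval beside the planned model, outside the Benjamini-Hochberg family, with no rule that both must be significant. State its assumptions: roughly linear drift, and no carry-over or hormone-withdrawal effect at week 10. Give the −0.73c sensitivity.
4. **Supporting data.** Report saliva E2 and P4 at T2 and week 10. These can show incomplete suppression or residual hormone, but not a behavioural withdrawal effect. Confirm that the check-in EPSI uses the previous-week recall that section 6 describes for T1 to T4.

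Cost: SAP wording and a few extra models on data already scheduled, with no new visits or participants. The downside is more cautious wording for the Lupron-alone and T1 contrasts.

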To date, the effects of ovarian hormones on eating behaviors have been inferred from animal studies and from changes in behavior occurring with presumed and measured levels of hormones during the menstrual cycle. Although animal studies established that E2 controls eating behaviors,^{8, 9} studies have limitations: it is unclear if animal studies can translate to human behavior and observational human studies cannot conclude causality or tease apart the effects of E2 and P4 given the presence of both. Moreover, the neurobiological mechanisms underlying *why* ovarian hormones are responsible for symptom fluctuation remains unknown. E2 has pronounced effects on certain neuropathways¹⁹⁻²¹ and neurotransmitters^{22, 23} and in particular, may influence binge eating through its effect on reward processes that are altered in BN.²⁴⁻²⁶ Women with BN show reduced brain activation in dopamine-related reward pathways,²⁷ increased reward sensitivity,^{28, 29} and inhibitory control deficits³⁰ compared with healthy controls, which together, may result in increased reward-motivated behaviors (e.g., binge eating). Indeed, E2 replacement in ovariectomized rats decreases food reward-motivated behavior³¹ and, in women, delay gratification is inversely associated with E2³² whereas E2 suppression reduces reward responsivity.³³ Together, this suggests E2 neuromodulation of aspects of the reward response may be responsible for changes in binge eating observed across the menstrual cycle.

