This also standardizes each study phase to be 2-weeks in length as the first month of Lupron is not a study phase of interest, yet a ‘waiting period’ for ovarian suppression to occur.

Table 4. Study Visit Procedures

| Procedure | T0 | T1 | T2 | T3 | T4 | T5 | Check-in |
|-----------------------------------|----|----|----|----|----|----|----------|
| Eligibility and Enrollment | | | | | | | |
| Informed Consent | x | | | | | | |
| Demographics | x | | | | | | |
| SCID-5 | x | | | | | | |
| GYN Exam/Medical History | x | | | | | | |
| Venipuncture | x | | | | | | |
| Saliva Samples | | x | x | x | x | | x |
| Side Effects & Adherence | | | x | x | x | | x |
| Self-report Questionnaires | | | | | | | |
| IDAS* | x | x | x | x | x | x | x |
| EDEQ* | x | x | x | x | x | x | x |
| EPSI | x | x | x | x | x | x | x |
| BIS/BAS | | x | x | x | x | x | x |
| SPSRQ | | x | x | x | x | x | x |
| Behavioral Tasks | | | | | | | |
| MIDT | | x | x | x | x | | |
| DD | | x | x | x | x | | |
| Go/No Go | | x | x | x | x | | |
| PANAS | | x | x | x | x | | |
| 24-hour Food Intake | | x | x | x | x | | |

*used to monitor subject safety only

Induced Hypogonadism. At T1, participants will receive their first injection of the gonadotropin-releasing hormone (GnRH) agonist leuprolide acetate (Lupron) 3.75 mg/month via i.m. injection, which is administered to produce a stable hypogonadal condition (after the initial “flair”). The first Lupron injection will be administered at approximately day six of the participants’ first menstrual cycle and monthly thereafter. Subjects will be on Lupron alone for 6-weeks. Previous studies using this experimental design show significant change in behavioral measures of interest after 6-weeks.⁸⁷

During the first month of GnRH agonist administration, participants will not receive any other medication. After 4-weeks of Lupron alone, all participants will receive 2-weeks of placebo capsules (blinded to the participant) and continue daily capsules throughout the duration of the study. Subjects will be told at some points the medication will be active and at other points it will be placebo. Subjects will not know when medication is active vs. placebo. An end-of-phase (T2) assessment will occur before addback, 2-weeks after medication administration begins.

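### Aim 2 tests the null of no E2 effect partly with E2 versus the pre-drug baseline (T1), a contrast that mixes the Lupron effect with the E2 effect

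*Combined protocol and SAP*

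**What the plan says.** Section 7.2 (Hypothesis) states: "our null hypothesis is that there is no effect of E2 on binge eating or the reward response". Aim 2 is to "Determine the effect of E2 on reward response and related correlates", and its tests are given in one sentence: "The contrasts between E2 and baseline (T1) or Lupron-alone (T2) will be tested in the same model". Nothing says which of the two contrasts decides the aim.

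Aim 1 is more careful. It treats E2 vs Lupron-alone, E2 vs P4 and P4 vs Lupron-alone as the primary contrasts, and calls comparisons with baseline additional. There the baseline is described as "baseline (T1), which occurs prior to medication administration".

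Section 6 places the first Lupron dose at T1 and continues Lupron throughout the challenge. On timing it says: "The first Lupron injection will be administered at approximately day six of the" first menstrual cycle. By the schedule in Sections 5.2 and 6, the E2 assessment falls after 8 or 12 weeks of Lupron, depending on sequence.

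Three other statements in Section 7.2 matter here:

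- Scoring in Aim 2: "For self-report questionnaires, a decrease in scores represents a beneficial response".
- Multiplicity: "For all hypothesis tests, we will use the Benjamini-Hochberg Procedure to correct for multiple comparisons". No family of tests is defined.
- The mediation exploration opens if the alternative hypotheses of both Aims 1 and 2 are supported.

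**The concern.** A test of no E2 effect should compare states that differ in E2. T1 and the E2 visit differ in two drugs. If E2 addback does nothing but Lupron alone moves the outcome, E2 vs T1 will tend to reject, and under the plan as written that rejection is one of two results bearing on the E2 null.

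The protocol gives reason to think that Lupron may move these outcomes. Section 1.1 cites evidence that "E2 suppression reduces reward responsivity". Since lower self-report scores count as benefit, a fall caused by removing E2 could be credited to giving E2.

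The opposite failure is also possible, and it is closer to the trial's own model. If low E2 worsens reward response and addback returns it to the T1 level, E2 vs T1 is about zero although E2 has acted.

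At stake are the attribution of an Aim 2 finding, the Aim 2 half of the condition for the mediation step, and the guidance this pilot gives to larger mechanistic trials.

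**Working it through.** **Inputs.** From Section 7.1: n = 15, two-sided 0.05, 80% power, detectable effect 0.77. From Sections 6 and 7.2: T1 before any drug, T2 on Lupron alone, E2 visit on Lupron plus E2. Assumed: the standardised paired Lupron shift on a reward outcome, shown as a range.

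**The plan's own figure.** For a paired t-test with df = 14, the critical value is 2.145 and the noncentrality is λ = d√15. At d = 0.77, λ = 0.77 × 3.873 = 2.98 and power is 79.2%. The effect giving exactly 80% is 0.778. The stated 0.77 is reproduced to rounding, so the paired test is a fair stand-in for the planned contrasts.

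**Decomposition.**

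E2 − T1 = (T2 − T1) + (E2 − T2)

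The first term is the change under Lupron alone and the second is the change on adding E2. Each also carries any time or practice effect between visits. Only the second term bears on the stated null.

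**False attribution.** Set E2 − T2 = 0, with no time or practice effect and complete data. Then P(reject E2 = T1) is the probability that a noncentral t (df 14, λ = shift × √15) falls beyond ±2.145:

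| Assumed Lupron shift (paired) | λ | P(reject E2 vs T1) | P(reject E2 vs T2) |
|---|---|---|---|
| 0 | 0 | 5.0% | 5% |
| 0.2 | 0.77 | 11.2% | 5% |
| 0.3 | 1.16 | 19.2% | 5% |
| 0.5 | 1.94 | 43.8% | 5% |
| 0.77 | 2.98 | 79.2% | 5% |
| 1.0 | 3.87 | 94.9% | 5% |

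A 40,000-run three-visit simulation (within-person correlation 0.5 assumed) agreed at the shifts it covered: 19.1%, 43.9%, 79.3% and 94.9% for shifts of 0.3, 0.5, 0.77 and 1.0, with E2 vs T2 at 4.8% to 5.0% throughout.

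**Does multiplicity correction help?** As an illustration only, applying Benjamini-Hochberg to just these two contrasts on one outcome still rejects E2 vs T1 in 12%, 32%, 68% and 90% of simulated trials at shifts of 0.3, 0.5, 0.77 and 1.0. It cannot cure the problem, because E2 = T1 is then a false null and is rejected correctly. What is wrong is the E2 label.

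**Masking.** Set T2 − T1 = −0.77 and E2 − T2 = +0.77 in paired SD units. Then E2 − T1 = 0 and E2 vs T1 rejects 5% of the time, while E2 vs T2 has 79.2% power for the same real effect.

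**The case against.** The strongest reply is that the right contrast is already in the plan. E2 vs Lupron-alone is tested in the same model and would expose a shift due only to Lupron. The hypothesis is worded around E2 addback in a low-E2 context, which points to T2, and Aim 2 borrows Aim 1's models, where baseline contrasts are additional. This stands in part. A reader might infer that the plan will report a Lupron effect as an E2 effect, but no text says that an E2-vs-T1 difference alone will be called one. Still, the Aim 2 sentence sets the two contrasts side by side, and borrowing a model does not clearly borrow a ranking.

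Other limits also stand:

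- **Size.** A reader might take the d = 1.51 cited for Lupron on food cravings and conclude that false rejection is near certain. It is not a suitable anchor. In Section 1.4 it reflects a fall from the premenstrual peak (week 4: 3.3, against 1.7 on the agonist) in women with PMS. T1 is at about day six, and the week-2 mean was 1.6 (SD 0.7), a difference of 0.1 from the agonist value. Taken as 0.1/0.7 with within-person correlation of 0 to 0.7, that is a paired shift of 0.10 to 0.18 and a rejection rate of about 7% to 10%. Week 2 is not exactly T1, and cravings are not reward, so this is no anchor either.
- **Direction.** A false benefit fits mainly the self-report scales. On the Monetary Incentive Delay task faster responding counts as benefit, so a Lupron-driven slowing would count against E2.
- **Multiplicity.** A reader might infer that Lupron-driven rejections loosen the threshold for the E2-vs-T2 tests. That requires pooling them in one family, which Section 7.2 does not specify, so any such figure would be illustrative.
- **Consequence.** Mediation needs Aim 1 as well, is exploratory, and sits in a 15-woman pilot.
- **The alternative contrast.** T2 always precedes addback, so E2 vs T2 carries time and practice effects. The randomised comparison is E2 vs P4.

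**Conclusion.** The point holds in a limited form and should be fixed. One of the two contrasts named for Aim 2 does not test the stated null. It can lead to a wrong attribution to E2 or hide a real restoration by E2, and the plan has no rule for which contrast decides.

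For any non-zero Lupron effect, E2 vs T1 rejects more than 5% of the time when E2 does nothing. How much more depends on a quantity the documents do not give: 11% at a paired shift of 0.2, 44% at 0.5 and 95% at 1.0. These rates assume 15 complete participants, a paired-t approximation to the mixed-model contrast, no time or practice effect, and no multiplicity correction. The 0.77 row uses the trial's detectable effect as a convenient value; it is not an estimate of what Lupron does.

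The documents do not support the stronger conclusion that Aim 2 will misreport Lupron effects as E2 effects.

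**What to change.** In Section 7.2, Aim 2:

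1. Name E2 vs Lupron-alone (T2) as the contrast that tests the E2 null and as the Aim 2 condition for the mediation step, giving Aim 2 a ranking as Aim 1 already has.
2. Report T2 vs T1 (the Lupron change) and E2 vs T1 (Lupron plus E2 versus pre-drug baseline) descriptively, with confidence intervals, outside the set of tests of the E2 null. The treatment factor as written has three levels and none for baseline, so the text should say how the T1 contrasts are estimated.
3. State that a difference from T1 is not by itself evidence of an E2 effect. Aim 3's change scores run from baseline to E2 addback and need the same caution.
4. State that E2 vs T2 has a fixed order, so time and practice effects remain.

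The cost is a few sentences. No new data or participants are needed, and the detectable effect for E2 vs T2 stays at about 0.78 with n = 15 and 80% power. The downside is that E2 vs T1 can no longer be claimed as an E2 finding.
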